#### 15.3.5.1. Healthcare Resource Utilization

The number of physician's office visits, ER visits, and hospitalizations (for any reason and those related to schizophrenia) per month at PS Baseline, OLE Baseline, and each scheduled extension visit will be summarized, as well as the average length of hospital stays (for any reason and those related to schizophrenia) at these time points. The frequency and percentage of subjects receiving unpaid care at PS Baseline, OLE Baseline, and each scheduled extension visit, along with the average number of hours a caregiver spends per week helping the subject at these time points, will also be summarized.

The change in the number of physician's office visits, ER visits, and hospitalizations, the average length of hospital stays, and the average number of hours a caregiver spends per week helping the subject from the PS Baseline and from the OLE Baseline at each scheduled extension visit will be summarized. Shifts from the PS Baseline and from the OLE Baseline to each scheduled extension visit in whether the subject receive unpaid care will also be summarized.

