### **Study Design:**

This is a 24-week, outpatient, multicenter, flexible-dose, open-label extension study designed to evaluate the long-term safety and tolerability of SEP-363856 (50 to 100 mg/day) for the treatment of subjects with schizophrenia who have completed Study SEP361-308 treatment period, during which they were switched from a previous antipsychotic treatment to SEP-363856.

The study will consist of two periods: An open-label extension (OLE) Treatment Period (up to 24 weeks), and a Follow-up Period visit at  $7 \pm 2$  days after last study drug dose for subjects who complete the Treatment Period and those who prematurely discontinue from the study.

Subjects who meet the entry criteria and choose to enter the extension study will transition immediately at the End of Treatment (EOT) visit from Study SEP361-308. Subjects who early terminate (ET) from the SEP361-308 study are not eligible to enroll in SEP361-309. The EOT visit from Study SEP361-308 will serve as the OLE Baseline visit for the present study. Informed consent will be obtained from all subjects before any study procedures are performed for the present study.

Treatment Period will occur as shown in Figure 1 Study Schematic, during which the procedures outlined in Table 2 will be conducted. Subjects will attend a Baseline visit on Day 1 (same day as the EOT visit of Study SEP361-308).

Subjects will be seen at Baseline and then every 4 weeks thereafter up to Week 24. Telephone calls will be made by a qualified member of the clinical research staff to the subjects weekly between visits to administer the C-SSRS, collect AEs and concomitant medications, as well as to remind subjects about adherence to study drug administration and upcoming visits. Unscheduled visits may occur at the discretion of the investigator.

Overall study design details provided in Section 7.1.

**Number of Subjects (planned):** This study will only enroll subjects who have completed the treatment period of Study SEP361-308 which plans to enroll approximately 120 subjects. It is anticipated that approximately 67 subjects will enroll in Study SEP361-309, assuming 75% of the subjects in Study SEP361-308 complete that study and 75% of the completers will enroll in this study.

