#### 7.3.3. Rationale for the Endpoints

The objective of this study is to demonstrate that clinically stable outpatients with schizophrenia who have completed a switch from their current antipsychotic treatment can be safely and effectively maintained on open-label treatment with SEP-363856 for a period of 24 weeks. The outcome measures include standard safety measures (eg, AE's, SAE's, measures of motor function, assessment of suicidality, laboratory assessments, and ECGs). Additional validated effectiveness assessments for schizophrenia (eg, PANSS, CGI-S) that were also employed in Phase 2 and Phase 3 studies of SEP-363856 are included for the purpose of providing longer-term effectiveness data. Additionally, measures assessing function, medication satisfaction, quality of life, sleep, and healthcare utilization are intended to provide information on real-world and overall health aspects associated with transitioning between treatments.

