#### 11.4.8. Healthcare Resource Utilization

Healthcare resource utilization will be assessed by recording the following post Baseline:

- number of physician office visits, ER visits, and hospitalizations (total number and number related to schizophrenia) since prior assessment
- length of each hospital stay since prior assessment
- employment status since prior assessment
- the average number of hours a caregiver(s) spends helping the subject per week (since prior assessment)

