# 15.1. Sample Size

All subjects who complete SEP361-308 are eligible to enroll. It is anticipated that approximately 67 subjects will enroll in this study (SEP361-309), assuming 75% of the subjects complete Study SEP361-308 and 75% of the completers will enroll in this study. The sample size is not based on statistical considerations.

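### Change in average length of hospital stay is defined for few subjects and does not follow inpatient burden; change in total inpatient days per subject-month would

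*Protocol*

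**What the plan says.** Long-term impact on healthcare resource utilisation (HCRU) is one of the objectives in Protocol Section 5.2, and length of hospital stays is one of the HCRU components among the other endpoints in Section 6.3.

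Section 15.3.5.1 has two parts that matter here.

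- The first paragraph summarises levels: "hospitalizations (for any reason and those related to schizophrenia) per month at PS Baseline, OLE Baseline, and each scheduled extension visit will be summarized". It does the same for average length of stay, again for any reason and for schizophrenia.
- The second paragraph summarises changes from both baselines. It opens with "The change in the number of physician's office visits, ER visits, and hospitalizations" and continues with "the average length of hospital stays, and the average number of hours a caregiver spends per week helping the subject from the PS Baseline", then names the OLE Baseline as the second reference.

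On the data side, Section 11.4.8 records the number of hospitalisations and the "length of each hospital stay since prior assessment". Table 2 places extension HCRU collection at Week 12 and at Week 24 or early termination.

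No section gives a value for a subject without a stay. Section 15.3.10 covers missing scale items and carrying the last observation forward to Week 24. No summary of total inpatient days is planned.

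**The concern.** An average length of stay is a ratio, days divided by stays, and has no value when there are no stays. Its change needs a stay in both periods. Section 7.3.3 describes the population as "clinically stable outpatients with schizophrenia who have completed a switch from their current antipsychotic treatment", so stays should be uncommon and stays in both periods rarer still. A subject admitted before the switch and never again, or admitted for the first time in the extension, contributes nothing to this line.

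There is a second difficulty, which no coding rule removes. The average ignores how many stays occurred, so it can stay flat or fall while days in hospital rise. At stake is whether the HCRU tables can say how days in hospital changed, which neither the count of admissions nor the average length shows.

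**Working it through.** **Expected sample size.** The parent study is one "which plans to enroll approximately 120 subjects" (synopsis), and Section 15.1 gives the rollover, "assuming 75% of the subjects complete Study SEP361-308 and 75% of the completers will enroll in this study". So 120 × 0.75 × 0.75 = 67.5, which agrees with the stated figure of about 67.

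**Subjects with a computable change if no stay means no value.** Let b be the risk of at least one stay in the baseline period and p the risk in a post-baseline period. The protocol gives neither. The ranges assumed are 2% to 30% for b and 2% to 20% for p.

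- Independent periods: expected n = 67 × b × p.
- Threefold post-baseline risk after a baseline stay, with p kept as the overall risk: expected n = 67 × b × 3p / (1 + 2b).

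| b / p | Independent | Threefold risk |
|---|---|---|
| 2% / 2% | 0.03 | 0.08 |
| 5% / 5% | 0.17 | 0.46 |
| 10% / 10% | 0.67 | 1.68 |
| 20% / 10% | 1.34 | 2.87 |
| 20% / 20% | 2.68 | 5.74 |
| 30% / 20% | 4.02 | 7.54 |

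Worked example for the last row: 67 × 0.30 × 0.20 = 4.02, and 67 × 0.30 × 0.60 / 1.60 = 7.54. The range is about 0 to 8 of 67.

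The chance of at least two computable values is 1% at 5%/5% and 15% at 10%/10% under independence, and 8% and 50% with threefold risk. Complete overlap of the two periods would set a ceiling of 67 times the smaller risk, for example 67 × 0.10 = 6.7.

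**Share of hospitalised subjects who drop out of the line.** Under independence, subjects with a stay in at least one period number 67 × (b + p − bp).

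- 5%/5%: 6.5, of whom 0.17 have a computable change.
- 10%/10%: 12.7, of whom 0.67 do.
- 20%/10%: 18.8, of whom 1.34 do.

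**Behaviour when the number of stays differs.** These two subjects have stays in both periods, so the zero convention does not affect them.

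- One 10-day stay, then three 10-day stays: the average goes from 10 to 10, a change of 0. Inpatient days go from 10 to 30.
- One 4-day stay, then stays of 4 and 2 days: the average goes from 4 to 3, an apparent reduction. Inpatient days go from 4 to 6, a rise of half.

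**The alternative.** Total inpatient days, counted as 0 when there was no stay, have a change value for every subject with HCRU data at both times, up to 67.

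**The case against.** The strongest reply is that the rest of Section 15.3.5.1 already shows what this line omits. Change in the number of hospitalisations stands in the same sentence: a subject with one stay before the switch and none later scores −1, and a first admission in the extension scores +1. Hospitalisations per month are also tabulated. A new admission generally meets an SAE criterion (Section 12.1.2), and SAE incidence is part of the primary endpoint. A reader might infer from the average-length line that the HCRU plan misses reduced or new inpatient use. The documents do not support that; the gap is confined to days in hospital.

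The next reply is that the handling of subjects without a stay is a derivation rule that may sit in the SAP, which is not shown. That stands as far as it goes: the protocol does not exclude zeros, and silence on the convention is not itself a fault. But zeros turn the quantity into something other than an average length of stay, and they leave the two multiple-stay examples unchanged. The weakness lies in the statistic the protocol names.

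Third, the protocol does not say whether the average is taken within subject or across all stays at a time point. If across stays, a group-level figure for days could be pieced together from the rate and the average. That is not planned and would give no subject-level change.

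Finally, this is a descriptive item in a single-arm study with no hypothesis test, and the primary safety result does not depend on it. That stands in full and limits the weight of the point.

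**Conclusion.** The point holds as a minor one. The planned change in average length of stay either rests on a small selected group or, with zeros, stops being an average length of stay. Under both conventions it can move differently from inpatient burden. No planned measure captures change in inpatient days, although the stay lengths needed are collected.

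The size, about 0 to 8 of 67, rests on assumed risks and on either independence or a threefold correlation. It also assumes that all 67 subjects supply HCRU data at both times; dropout would lower it. A reader might infer that only zero or one subject would have a value. That fits risks up to about 10% per period with weak correlation, but the protocol states no hospitalisation rate, so it cannot be asserted as the expected result.

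**What to change.** In Section 15.3.5.1, replace the change in average length of stay with the change in total inpatient days per subject-month from the PS Baseline and from the OLE Baseline. Report it for any reason and for schizophrenia, count 0 when there was no stay, and include all safety-population subjects with HCRU data at both times. Keep average length per stay only as a description of the stays that occurred, with the number of stays and subjects. Leave the change in number of hospitalisations as planned.

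The cost is a wording change in one section, carried into the SAP. No new data are needed: the length of each stay is already recorded, and the per-month scaling is already used for the counts.

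One related item should be settled at the same time. Table 2 takes the core-study HCRU value from the pre-switch baseline visit, whereas Section 11.6.1 lists HCRU among the core-study end-of-treatment procedures. Any change from the OLE Baseline, in days or otherwise, needs an OLE Baseline value to exist.

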#### 15.3.5.2. Nicotine Use Information

Nicotine use data will be summarized descriptively at each visit that it is scheduled for collection. For each nicotine type, the amount being used at each visit in comparison with the amount being used at Baseline will be classified as "increased", "decreased", or "unchanged" for every subject, based on the reported amount used in a given period.

Then for subjects whose changes in amount for all nicotine types between PS Baseline, OLE Baseline, and each scheduled post-OLE Baseline extension visit are not in opposite directions, a subject's overall nicotine consumption at each scheduled post-OLE Baseline extension visit in comparison with Baseline will be classified as "increased", "decreased", or "unchanged".

The number and percentage of subjects in each overall consumption amount change category will be summarized.

In addition, for subjects who reported using "Cigarettes" at either PS Baseline, OLE Baseline, or each scheduled post-OLE Baseline visit or at more than one of these time point, the amount of cigarette used per day and the change from Baseline values will be summarized at each scheduled post-OLE Baseline extension visit, based on both the PS Baseline and the OLE Baseline.

Further details regarding the specifics of this analysis will be described in the SAP.

## 15.3.5.3. Adjustment for Multiplicity

Not applicable as only descriptive statistics for effectiveness parameters will be compiled.

#### 15.3.6. Safety Analyses

#### 15.3.6.1. Analysis of Primary Endpoint

The primary endpoint is the incidence of overall AEs, SAEs, and AEs leading to discontinuation. The incidence will be calculated by a proportion consisting of the number of subjects who experience these events (ie, AEs, SAEs, and AEs leading to discontinuation) as the numerator over the safety population as the denominator along with a corresponding 95% confidence interval (CI).

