The current standard of care for the treatment of schizophrenia is the use of second generation antipsychotics or "atypical antipsychotics" (Lehman-2004; Kreyenbuhl-2009; Meltzer-2011; Nakamura-2009). These "atypicals" are thought to have fewer extrapyramidal side effects compared to first generation antipsychotics or "typical antipsychotics" (eg, haloperidol) (Leucht-2009; Naber-2009). However, some patients respond poorly to both atypical and typical antipsychotics, and some continue to have symptoms and substantial functional/cognitive impairment (Keefe-2006; Webber-2008). Very few patients return to baseline (pre-psychosis) function (Schultz-1999; Pearlson-2000; Kapur-2001). In addition, some atypical agents are associated with a variety of other side effects, including weight gain, metabolic syndrome, sedation, QTc prolongation, extrapyramidal symptoms and tardive dyskinesia (Davis-2004; Lieberman-2005; Newcomer-2007; Leucht-2009), which may lead to significant comorbid medical problems as well as contribute to poor compliance and treatment discontinuation.

The large-scale NIMH-CATIE schizophrenia study found that 70% to 80% of outpatients discontinue medications before 18 months because of lack of efficacy or occurrence of side effects (Lieberman-2005). Noncompliance often leads to relapse of symptoms and the need for rehospitalization (Ascher-Svanum-2010; Munro-2011; Morken-2008). Clearly, an unmet need exists for new, effective, and well-tolerated treatments for schizophrenia.

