### 7. INVESTIGATIONAL PLAN

## 7.1. Overall Study Design

This is a 24-week, outpatient, multicenter, flexible-dose, open-label extension study designed to evaluate the long-term safety and tolerability of SEP-363856 (50 to 100 mg/day) for the treatment of subjects with schizophrenia who have completed Study SEP361-308 treatment period, during which they were switched from a previous antipsychotic treatment to SEP-363856.

The study will consist of two periods: An open-label extension (OLE) Treatment Period (up to 24 weeks), and a Follow-up Period visit at  $7 \pm 2$  days after last study drug dose for subjects who complete the Treatment Period and those who prematurely discontinue from the study (Figure 1).

Subjects who meet the entry criteria and choose to enter the extension study will transition immediately at the End of Treatment (EOT) visit from Study SEP361-308. Subjects who early terminate (ET) from the SEP361-308 study are not eligible to enroll in SEP361-309. The EOT visit from Study SEP361-308 will serve as the OLE Baseline visit for the present study. Informed consent will be obtained from all subjects before any study procedures are performed for the present study.

A study schematic is presented in Figure 1. Details of the study assessments and other procedures to be performed at each visit are presented in Table 2 Schedule of Assessments, and Section 11.6, Study Visits and Assessments. If necessary, subjects may return to the clinic at any time for an unscheduled visit at the discretion of the investigator.

Subjects will attend a Baseline visit on Day 1 (same day as the EOT visit of Study SEP361-308). Subjects will be seen at Baseline and then every 4 weeks thereafter up to Week 24. Telephone calls will be made by a qualified member of the clinical research staff to the subjects weekly between visits to administer the C-SSRS, collect AEs and concomitant medications, as well as to remind subjects about adherence to study drug administration and upcoming visits.

[figure not shown]

Figure 1: Study Schematic

Abbreviations: OLE = open-label extension.

All subjects will begin by receiving open-label SEP-363856 at the same dose they were taking upon completion of Study SEP361-308. Thereafter, the dose can be adjusted within the range of 50 to 100 mg/day, if deemed clinically necessary by the Investigator.

Dose adjustment criteria for SEP-363856 are described in Section 10.1.1.

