# 15.2. Analysis Populations

# **15.2.1.** Safety Population

The safety population will consist of all subjects who receive at least one dose of study drug during the 24-week OLE treatment period. The Safety Population will be used for the long-term safety, tolerability, and effectiveness analyses.

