## 15.3.2. Study Drug Exposure and Compliance

Duration of exposure and compliance during the open-label extension treatment period will be summarized for the safety population.

Duration of exposure (in days) will be calculated as: last extension study dose date - first extension study dose date + 1. Duration of exposure will be summarized both as a continuous variable and categorically:

- Number and percentage of subjects with the open-label extension study drug exposure  $\geq 1, \geq 14, \geq 28, \geq 42, \geq 90, \geq 120, \geq 150$  days;
- Number and percentage of subjects with the open-label extension study drug exposure for 1 13, 14 27, 28 41, 42 89, 90 119, 120 149,  $\ge 150$  days

Percent compliance will be calculated overall for the open-label extension treatment period as: (number of tablets taken / number of tablets should have been taken)  $\times$  100%. Non-compliance is defined as less than 75% or more than 125% non-missing compliance for the open-label extension treatment period. Subjects with missing compliance will not be classified as non-compliant. Percent compliance will be summarized both as a continuous variable and

categorically (ie, number and percentage of subjects in each compliance category: < 75%, 75% - 125%, > 125%, and missing).

Mean daily dose will be calculated for the entire open-label extension treatment period as the cumulative dose (mg) of SEP-363856 divided by the duration of exposure (in days), where cumulative dose is the sum of all doses a subject received during the open-label extension treatment period. Modal daily dose will be determined as the daily dose that is taken for the most time (in terms of number of days) among all doses taken. Both mean daily dose and modal daily dose will be summarized.

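### The primary AE analysis is a crude proportion over all treated subjects; if read as 24-week risk it understates AE and SAE risk, so estimates based on time at risk should be added

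*Protocol*

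**What the plan says.** Protocol Section 15.3.6.1: "The primary endpoint is the incidence of overall AEs, SAEs, and AEs leading to discontinuation". The estimator follows: "The incidence will be calculated by a proportion consisting of the number of subjects who experience these events", "over the safety population as the denominator along with a corresponding 95% confidence interval (CI".

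Other sections determine how that estimator behaves:

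- **Denominator.** Section 15.2.1: "The safety population will consist of all subjects who receive at least one dose of study drug during the 24-week OLE treatment period". No minimum exposure is required.
- **Observation time.** Section 13.1 takes subjects off study once they stop study drug and does not replace them. Section 13.2 then leaves only the early-termination visit and one follow-up visit 7 ± 2 days after the last dose.
- **AE tables.** Section 15.3.6.2 uses the term incidence rate, but for a count of subjects, each counted once per system organ class and preferred term. AEs that start after the last dose are summarized separately.
- **Exposure.** Section 15.3.2: "Duration of exposure (in days) will be calculated as: last extension study dose date" minus the first such date, plus 1. Duration is tabulated in bands from 1–13 days to 150 days or more, but no AE summary uses it as time at risk.

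Section 15 leaves details of method to the SAP, which is not available here.

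**The concern.** The primary objective (Section 5.1) is long-term safety, and Section 7.1 sets the period: "This is a 24-week, outpatient, multicenter, flexible-dose, open-label extension study". The natural question is how many subjects would have an AE or SAE over 24 weeks of treatment. With a subject-count numerator and an all-treated denominator, a subject who leaves at Week 3 without an event contributes exactly what a 24-week event-free completer contributes. Whenever there is dropout, the proportion falls below the 24-week risk, which is the favourable direction, and its confidence interval does not reflect the shortfall. Section 15.3.10 sets a last-observation rule for missing Week 24 values but says nothing about early exit for the primary endpoint.

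**Working it through.** **1. The plan's own figure.** The core study is one "which plans to enroll approximately 120 subjects" (Synopsis). With 75% completing and 75% of completers rolling over (Section 15.1), 120 × 0.75 × 0.75 = 67.5. This matches the stated figure of approximately 67.

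**2. Inputs that have to be assumed.** The protocol states no dropout rate, AE rate or SAE rate for this study. Let *p* be the true 24-week risk of a first event and *d* the 24-week dropout, assumed independent of the event.

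**3. Constant hazards.** Over 24 weeks the cumulative hazards are a = −ln(1 − p) for the event and b = −ln(1 − d) for dropout. The expected crude proportion is

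crude = a/(a + b) × [1 − (1 − p)(1 − d)].

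Example with p = 0.50 and d = 0.30: a = 0.693, b = 0.357, so crude = 0.660 × (1 − 0.35) = 0.429.

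| Dropout *d* | Mean weeks before dropout or Week 24 | Crude if p = 5% | Crude if p = 10% | Crude if p = 50% | Crude ÷ p |
|---|---|---|---|---|---|
| 10% | 22.8 | 4.75% | 9.50% | 47.7% | 0.95–0.96 |
| 20% | 21.5 | 4.49% | 8.98% | 45.4% | 0.90–0.91 |
| 30% | 20.2 | 4.21% | 8.44% | 42.9% | 0.84–0.86 |
| 40% | 18.8 | 3.92% | 7.87% | 40.3% | 0.78–0.81 |
| 50% | 17.3 | 3.62% | 7.26% | 37.5% | 0.72–0.75 |

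**4. Early onset.** Put 80% of the event hazard in the first 4 weeks (an assumption). For p = 50% the crude figure is 48.41%, 47.52% and 46.55% at 20%, 30% and 40% dropout, or 0.97, 0.95 and 0.93 of the true risk. For p = 5% with the same pattern the ratios are 0.96, 0.94 and 0.92. Most of the gap closes because most events occur before most exits.

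**5. Scale at N = 67.** At 30% dropout and constant hazards, a 5% SAE risk loses 0.79 points (0.53 of a subject) and a 50% AE risk loses 7.08 points (4.75 subjects). For comparison, the exact 95% confidence interval is 0.9% to 12.5% for 3/67 and 38.2% to 63.2% for 34/67.

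**6. Who is miscounted.** Only leavers without a prior event are. A subject who has an AE or SAE and then leaves is already in that numerator. For AEs leading to discontinuation, an AE-caused exit is itself the event, so only exits for other reasons are in question.

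**The case against.** The protocol contains no misstatement. It defines incidence as a proportion, says how to compute it, and never calls the result a 24-week cumulative risk. The study is descriptive and has no power basis. Disposition and exposure duration will be reported, so a reader can see retention. Exposure-adjusted supplements are commonly left to the SAP, and Section 15.3.6.1 excludes none. All of this stands. It means the point is an improvement to a stated rule, not the correction of an error. It does not remove the point, because Section 15.3.6.1 does fix the estimator for the primary endpoint, and what it fixes is not a 24-week risk.

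A reader might infer three stronger things that the documents do not support:

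- **A specific large bias.** Section 4.1 cites an outpatient study in which "70% to 80% of outpatients discontinue medications before 18 months". At constant hazard that scales to −ln(0.3)/18 = 0.0669 and −ln(0.2)/18 = 0.0894 per month. Over 24 weeks (5.52 months) this is 31% to 39% dropout, which would turn a 50% risk into about 43% to 41% and a 10% risk into about 8.4% to 7.9%. The arithmetic is right, but the input is borrowed. Those were other medications, while subjects here have already completed 8 weeks and chosen to continue. The same sentence attributes the discontinuations to lack of efficacy or side effects, which conflicts with independent dropout. With early onset as in step 4, the same dropout gives about 47% and 9.2% to 9.4%.
- **That the AE analysis ignores exposure altogether.** Section 15.3.6.2 summarizes AEs by modal daily dose, which is derived from days at each dose. It is time at risk that is unused.
- **That the primary analysis is invalid.** It is a valid summary of what was observed on treatment.

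One point cuts against the premise. The consent text in Section 17.3 expects participation to continue after drug is stopped. Section 13.1 is explicit the other way, and Section 13.2 schedules only the two closing visits.

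**Conclusion.** The point holds as a qualified one. The crude proportion understates AE and SAE risk when read as 24-week risk, because early leavers without a prior event count as full non-events. Under independent dropout of 10% to 40% and constant hazards it is about 95% down to about 80% of that risk. With mostly early onset it is about 93% to 97% for any AE at 20% to 40% dropout. For any AE the gap can reach several percentage points. For SAEs it is about one subject or less at N = 67 for a 5% risk, and small beside the confidence interval. These figures rest on assumed dropout, event rates and onset patterns, since the protocol gives none. Whether the SAP already adds estimates based on time at risk cannot be known from the protocol.

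**What to change.** Keep the crude proportion and describe it as the proportion of subjects with an event during observed treatment. Add to Section 15.3.6.1:

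- **Any AE and SAE:** subjects with a first event per 100 subject-years at risk, with 95% CI, and the cumulative incidence to Day 169 with early exit censored. Count time at risk from the first extension dose to the first event or the last extension dose, to match the separate handling of post-treatment AEs.
- **AEs leading to discontinuation:** cumulative incidence with exits for other reasons treated as competing events. If every early exit is classified this way and nobody else is censored, this nearly reproduces the crude proportion. The gain for this component is an explicit definition rather than a different number.
- **Interpretation:** base any statement about 24-week risk on these estimates.

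AE and dosing dates are already collected, so no new visits, data or subjects are needed. The cost is one extra table and some wording. The rate assumes a roughly constant hazard, which early-onset AEs would strain. The censored cumulative incidence assumes non-informative dropout, which exits for lack of efficacy may strain. The reported risk will look slightly less favourable.
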